3.2.1.1 Inclusion Criteria

- ≥ 2 ICD-10-CM COPD diagnosis codes at least 30 days apart during the 12-month baseline period. Diagnosis codes are shown below in Figure 2.

Figure 2 – Diagnosis Codes for COPD

Code	Type	Description
J40	ICD-10 Dx	Bronchitis, not specified as acute or chronic
J410	ICD-10 Dx	Simple chronic bronchitis
J411	ICD-10 Dx	Mucopurulent chronic bronchitis
J418	ICD-10 Dx	Mixed simple and mucopurulent chronic bronchitis
J42	ICD-10 Dx	Unspecified chronic bronchitis
J430	ICD-10 Dx	Unilateral pulmonary emphysema (MacLeod's syndrome)
J431	ICD-10 Dx	Panlobular emphysema
J432	ICD-10 Dx	Centrilobular emphysema
J438	ICD-10 Dx	Other emphysema
J439	ICD-10 Dx	Emphysema, unspecified
J440	ICD-10 Dx	Chronic obstructive pulmonary disease
J441	ICD-10 Dx	Chronic obstructive pulmonary disease with (acute) exacerbation
J449	ICD-10 Dx	Chronic obstructive pulmonary disease, unspecified

- ≥ 1 pharmacy claim in the 6 months closest to sample identification for either UMEC/VI or FLUT/SAL fixed-dose single-inhaler dual therapy COPD treatments shown in Figure 3 and no claims for these treatments in the first 6 months of the sample identification period.

Figure 3 – COPD Medications for Sample Inclusion

Subclass	Medication	NDC Codes
LABA/anticholinergic	umeclidinium/vilanterol 62.5/25 mcg single-inhaler therapy	00173086906 00173086910
ICS/LABA	fluticasone/salmeterol 250/50 mcg single-inhaler therapy	68258303101 00173069604 23490754201 49999081960 21695019601 55045368601 68115092460 58016460401 54569524200 54868451700 00173069602 00173069600

- Age 65 and older
- Continuous enrollment during the 12-month baseline at the time of sample identification
- Self-reported health care provider diagnosis of COPD
- Self-reported treatment with FLUT/SAL or UMEC/VI
- Ability to complete the study survey in English

3.2.1.2 Exclusion Criteria

- Patients with ≥2 diagnosis codes for asthma at least 30 days apart in the 12-month baseline period will be excluded. ICD-10-CM codes for identifying asthma are shown in Figure 4.

Figure 4 – Diagnosis Codes for Asthma

Code	Type	Description
J4520	ICD-10 Dx	Mild intermittent asthma, uncomplicated
J4521	ICD-10 Dx	Mild intermittent asthma with (acute) exacerbation
J4522	ICD-10 Dx	Mild intermittent asthma with status asthmaticus
J4530	ICD-10 Dx	Mild persistent asthma, uncomplicated
J4531	ICD-10 Dx	Mild persistent asthma with (acute) exacerbation
J4532	ICD-10 Dx	Mild persistent asthma with status asthmaticus
J4540	ICD-10 Dx	Moderate persistent asthma, uncomplicated
J4541	ICD-10 Dx	Moderate persistent asthma with (acute) exacerbation
J4542	ICD-10 Dx	Moderate persistent asthma with status asthmaticus
J4550	ICD-10 Dx	Severe persistent asthma, uncomplicated
J4551	ICD-10 Dx	Severe persistent asthma with (acute) exacerbation
J4552	ICD-10 Dx	Severe persistent asthma with status asthmaticus
J45901	ICD-10 Dx	Unspecified asthma with (acute) exacerbation
J45902	ICD-10 Dx	Unspecified asthma with status asthmaticus
J45909	ICD-10 Dx	Unspecified asthma, uncomplicated
J45990	ICD-10 Dx	Exercise induced bronchospasm
J45991	ICD-10 Dx	Cough variant asthma
J45998	ICD-10 Dx	Other asthma

- Patients with claims for both UMEC/VI and FLUT/SAL in the 6 months closest to sample identification will be excluded.
- Patients with claims for triple therapy will be excluded.
 - Triple therapy is defined as claims for formulations of ICS/LABA/LAMA, including combined monotherapy formulations and fixed dose combinations (FDC).
 - The impact of using same day fills, or 30 days, or 60 days between fills will be assessed at the time of sample identification.
- Patients with claims-based evidence of diagnosis or treatment for lung cancer during the 12-month baseline will be excluded from the final analytic sample following the claims lag.

Some exclusion criteria cannot be applied until after survey data collection and/or the medical claims lag are complete (e.g., patient-reported diagnosis and treatment, evidence of lung cancer). Criteria that can be applied at the time of sample identification will be applied at that time.

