Study Design	This is a claims-linked cross-sectional observational survey study of Medicare Advantage (MA) enrollees of a large US health plan with evidence of COPD and single-inhaler dual therapy treatments FLUT/SAL or UMEC/VI. Patients will be recruited using Optum's health plan recruitment strategy. For this approach, patients will be identified in the Optum Research Database (ORD) following receipt of the appropriate approvals. Patients will complete a mailed cross-sectional survey to collect information on patients' condition history, current treatment, smoking history, symptoms and symptom severity (mMRC and CAT), and demographic and sociodemographic characteristics. Patient survey and diary responses are linked to medical and pharmacy claims for the 12-month period prior to the survey (baseline). A 30-35% response rate is estimated based on previous patient survey studies. Two waves of data collection are anticipated to meet the target sample size based on patient counts and estimated response rate. Descriptive and multivariable techniques are used for analysis.
Study Population and Sampling Methods	
Inclusion Criteria:
 
 ≥2 ICD-10-CM diagnosis codes for COPD at least 30 days apart during the 12 month period prior to sample identification 
 Diagnosis codes J40-J44 will be included ≥1 pharmacy claim for UMEC/VI or FLUT/SAL single-inhaler dual therapy during baseline Age ≥ 65 Self-reported health care provider diagnosis of COPD Self-reported prescription for FLUT/SAL or UMEC/VI 12 months of continuous enrollment during the baseline period Ability to complete the study survey in English 
Exclusion criteria:

	
 12 month period prior to sample identification Claims for both UMEC/VI and FLUT/SAL in the 6 months closest to sample identification Claims for triple therapy (ICS + LAMA + LABA) during the baseline period Evidence of lung cancer diagnosis and/or treatment
Data Source	
The ORD includes enrollment, pharmacy, and medical claims data from a large U.S. health plan affiliated with Optum to identify eligible adult participants. The individuals covered by this health plan are geographically diverse across the US.

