regular treatment with one or more long-acting bronchodilators as the disease progresses.¹¹ Inhaled long-acting bronchodilators, which include long-acting anticholinergics and long-acting β -agonists (LABAs), improve the airflow obstruction that characterizes COPD.

Dual therapies combined into single-inhaler, fixed dose delivery systems are important to examine in the context of simplifying treatment, improving adherence and quality of life, and managing disease progression. Umeclidinium/vilanterol (UMEC/VI 62.5/25 mcg; Anoro® Ellipta®) is a once-daily single inhaler dual LAMA/LABA therapy that was FDA-approved for the treatment of COPD in December 2013. Fluticasone/salmeterol (FLUT/SAL 250/50 mcg; Advair® Diskus®) is a twice-daily single inhaler dual therapy ICS/LABA treatment approved by the FDA for COPD treatment in November 2003. To better understand variation in burden of illness associated with these treatments, this study will provide evidence about associations between symptoms, clinical, economic, and sociodemographic characteristics, and GOLD classification for patients treated with UMEC/VI as compared to those treated with FLUT/SAL. Results of the study may be of interest to health care providers treating COPD patients and to third party payers.

The overall purpose of this study is to describe patient-reported symptom severity and claims-based healthcare utilization and costs among COPD patients treated with UMEC/VI or FLUT/SAL single-inhaler dual therapies in a real-world setting.

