3.3.3 Medicare Advantage Data Source

Medical and pharmacy claims data are available for approximately 4.2 million enrollees since 2006 that are enrolled in Medicare Part C (commonly referred to as the Medicare Advantage program) through an offering associated with Optum. Prior to 2006, data were available for approximately 500,000 of these enrollees. Medicare Advantage enrollees choose to receive all of their health care services through a provider organization in lieu of Medicare Part A/B coverage (commonly referred to as Medicare Fee for Service).

Claims for pharmacy services are typically submitted electronically by the pharmacy at the time prescriptions are filled. The claims history is a profile of all outpatient prescription pharmacy services provided and covered by the health plan. Pharmacy claims data include drug name, dosage form, drug strength, fill date, days of supply, financial information, and de-identified patient and prescriber codes, allowing for longitudinal tracking of medication refill patterns and changes in medications.

Medical claims or encounter data are collected from all available health care sites (inpatient hospital, outpatient hospital, ED, physician's office, surgery center, etc.) for virtually all types of provided services, including specialty, preventive and office-based treatments. Medical claims and coding conform to insurance industry standards. Claims for ambulatory services submitted by individual providers, e.g., physicians, use the Health Care Financing Administration (HCFA)-1500 or Centers for Medicare and Medicaid Services (CMS)-1500 formats. Claims for facility services submitted by institutions, e.g., hospitals, use the Uniform Billing (UB)-82, UB-92, UB-04, or CMS-1450 formats. Medical claims include: multiple diagnosis codes recorded with the International Classification of Diseases, Tenth Revision, Clinical Modification (ICD-10-CM) diagnosis codes; procedures recorded with ICD-10-CM procedure codes, Current Procedural Terminology (CPT), or Healthcare Common Procedure Coding System (HCPCS) codes; site of service codes; provider specialty codes; revenue codes (for facilities); paid amounts; and other information. Facility claims do not generally include medications dispensed in hospital.

Pharmacy claims are typically added to the research database within six weeks of dispensing. Approximately six months following the delivery of services are required for complete medical data for MA enrollees.

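### If a 30- or 60-day window between fills defines triple therapy, a sequential switch counts as triple therapy and opposite switchers are dropped from the two cohorts

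*Combined protocol and SAP*

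**What the plan says.** Section 3.2.1.2 identifies triple therapy from drug classes seen in claims: "Triple therapy is defined as claims for formulations of ICS/LABA/LAMA, including combined monotherapy formulations and fixed dose combinations (FDC"). On timing it says only: "The impact of using same day fills, or 30 days, or 60 days between fills will be assessed at the time of sample identification". It states no period for the exclusion and no criterion for choosing among the three spacings. The synopsis words the exclusion as "Claims for triple therapy (ICS + LAMA + LABA) during the baseline period", with no spacing at all.

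Three other passages matter:

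- Section 1 describes UMEC/VI as a "once-daily single inhaler dual LAMA/LABA therapy" and FLUT/SAL as a "twice-daily single inhaler dual therapy ICS/LABA treatment".
- Section 3.2.1.1 requires a claim for one study product in the last 6 months and "no claims for these treatments in the first 6 months of the sample identification period". This washout covers the two Figure 3 products only. Other LAMA, ICS, ICS/LABA and LAMA/LABA products are not barred.
- A separate rule in 3.2.1.2 handles switches between the study drugs: "Patients with claims for both UMEC/VI and FLUT/SAL in the 6 months closest to sample identification will be excluded".

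Sections 3.2.2 and 4.4 rely on inverse probability of treatment weighting, with the covariates in Appendix 4. That list has counts of medication fills but no class of prior maintenance therapy.

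**The concern.** Every patient starts the study drug in the second half of the 12-month window and may have come from another maintenance inhaler. Each study drug supplies two of the three classes, and the missing class differs: UMEC/VI lacks an ICS, and FLUT/SAL lacks a LAMA. A rule based on days between fills therefore cannot tell a last fill of an abandoned drug from joint use, and it treats the same prior drug differently in the two cohorts.

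At stake is the primary objective, a weighted comparison of symptom burden between the cohorts. If eligibility removes a type of patient from one cohort only, no weight can restore that type. The opposite error also matters: a rule too narrow to find triple users leaves them in a comparison of dual therapies.

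**Working it through.** **Inputs.** Drug classes from section 1; triple-therapy definition and spacing options from 3.2.1.2; washout from 3.2.1.1; covariates from Appendix 4; counts from Table 1; frame size from 3.5. I read a spacing rule as the days from the last prior fill to the first study-drug fill, with one such pair of fills sufficient.

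**Step 1: the plan's own counts.** Table 1 adds up: 977 + 1,064 + 29 = 2,070. The 29 had both study drugs. There is no row for triple therapy or for prior class.

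**Step 2: prior fill inside the window, prior drug then stopped.** A patient is excluded when prior and study drug together cover ICS, LABA and LAMA.

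| Prior product | Starts UMEC/VI | Starts FLUT/SAL |
|---|---|---|
| LAMA alone | kept | excluded |
| Other LAMA/LABA | kept | excluded |
| ICS alone | excluded | kept |
| Other ICS/LABA | excluded | kept |
| LABA alone | kept | kept |
| None | kept | kept |

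None of these patients used the three classes together by design. In the two LAMA rows the probability of being in the FLUT/SAL cohort is 0; in the two ICS rows the probability of being in the UMEC/VI cohort is 0. The inverse of 0 does not exist, so no weighted contrast can be formed in those strata.

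**Step 3: gap against spacing option, for the four cross-class switches above.**

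| Gap (days) | Same day | 30 days | 60 days |
|---|---|---|---|
| 28 | kept | excluded | excluded |
| 31 | kept | kept | excluded |
| 45 | kept | kept | excluded |
| 75 | kept | kept | kept |

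The gap depends on days of supply, which the documents do not give. With an assumed 30-day supply, an immediate switch has a gap of about 30 days: borderline under the 30-day option, inside the 60-day one. With an assumed 90-day supply the gap is about 90 days, and the switch passes all three options.

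**Step 4: would the planned diagnostics show it?** Section 4.4 inspects histograms of the fitted propensity score, its goodness of fit, and weighted against unweighted p values for the included covariates. Prior class is not a covariate, so the fitted score averages over it. The histograms can overlap well while the strata in step 2 are one-sided.

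**Step 5: what can be sized.** If a share s of each cohort were removed (assumption, 5% to 30%), the Table 1 counts would become:

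- s = 5%: 977 × 0.95 = 928 and 1,064 × 0.95 = 1,011
- s = 30%: 977 × 0.70 = 684 and 1,064 × 0.70 = 745

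The frame needed is 1,350 per cohort over the planned waves. These figures show the cost to the frame for a given s; they do not estimate s.

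The direction of bias is likewise open. Let a be the share of the UMEC/VI cohort with a recent LAMA, and dL the difference in their mean CAT score from the rest; let b and dI be the same for recent ICS in the FLUT/SAL cohort. The induced difference is a × dL − b × dI. With a = b = 0.3 (assumed):

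- dL = 2, dI = 0: 0.3 × 2 − 0.3 × 0 = 0.6
- dL = 2, dI = 2: 0.3 × 2 − 0.3 × 2 = 0
- dL = 0, dI = 2: 0.3 × 0 − 0.3 × 2 = −0.6

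The sign turns on inputs that the documents do not contain.

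**The case against.** The strongest reply is that no window has been adopted. The sponsor has flagged the spacing question, section 3.3.2 defers claims algorithms to the SAP, and under the same-day option no sequential switch is excluded. That stands, and the point is conditional for this reason. It does not dispose of the matter: two of the three listed options produce the pattern in step 2, and the third keeps a true triple user who collects inhalers on different days. None of them separates a switch from joint use.

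A reader might infer that the cohorts would have no overlap in prior therapy. The documents do not support that. Non-overlap is confined to LAMA or ICS fills inside the window. Patients with no recent maintenance therapy, LABA alone, or an older fill are found in both cohorts. Switches between the two study drugs are already removed by their own rule.

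The survey is a partial safeguard against triple users kept by the same-day option. Section 3.3.1.1 collects current COPD treatment, and self-reported use of a study drug is an inclusion criterion. But the documents do not say that respondents reporting three classes are excluded.

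The secondary objective mentions treatment history, so a descriptive table might reveal prior class. Nothing ties that to the weighting.

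A rule based on supply overlap has its own gap. One study-drug claim suffices, and section 3.1.5 makes the identification and observation periods the same 12 months. If 30 days of overlap were required, patients starting in the last 30 days could not show it. With starts uniform over about 182 days (assumption), that is 30/182, or about 16%. This objection stands and shapes the fix.

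**Conclusion.** The concern holds conditionally. Under a 30- or 60-day window, the exclusion counts sequential switches as triple therapy and makes recent LAMA and recent ICS use one-sided between the cohorts. Weighting cannot correct this within those strata, and the planned diagnostics may miss it. Same-day spacing exchanges this for undetected triple users. If the synopsis wording is read literally, with no spacing, a switch at any gap within the baseline would count.

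A reader might also infer that a sizeable fraction of each cohort is lost, or that those removed are the most symptomatic. Neither follows. The documents give no share of switchers, no supply lengths and no symptom data by prior class, so the number affected and the size and direction of bias are unknown. The conclusion rests on one pair of fills being enough to qualify, which 3.2.1.2 does not rule out.

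**What to change.** Before sample identification:

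1. Replace the spacing options with concurrent use, applied identically to both cohorts. Triple therapy would be any fixed-dose triple fill, or overlapping supply of ICS, LABA and LAMA with the earlier drug refilled on or after the first study-drug fill. The fields exist: section 3.3.3 says "Pharmacy claims data include drug name, dosage form, drug strength, fill date, days of supply".
2. For patients who start too late in the window to show an overlap, use the survey's current-treatment item as a check, and state how a report of three classes is handled.
3. Tabulate exclusions by cohort and prior class under the new rule and under the 60-day rule.
4. Add prior maintenance class to the Appendix 4 covariates, so that retained switchers are balanced and any remaining one-sidedness becomes visible.
5. Reconcile the synopsis with 3.2.1.2 on the period and spacing.

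The cost is wording and programming on data already held, with no added patient contact; direct switchers stay in a scarce frame. The downside is that short overlaps are treated as switches. The minimum overlap length has no basis in the documents, so it should be set in advance and varied in a sensitivity analysis.

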3.2.2 Sampling

The study sample is not randomly selected. A convenience (e.g., non-random) sampling approach will be used. It is estimated that all eligible patients will be invited to participate in the study. Sufficient counts are not available to match patients on demographic characteristics at the time of sample identification; however, IPTW will be used to address potential confounding due to non-treatment characteristics (see Section 4.4).

3.3 Data Sources

3.3.1 Patient-reported Measures: Cross-sectional Survey

The cross-sectional survey will collect the following measures:

3.3.1.1 Patient Reported Clinical Characteristics

- **Diagnosis**—Patients will be asked to confirm that a doctor or other health care provider has told them they have COPD. Patients will be instructed to return but not complete the survey if they do not meet this criterion.
- **General health**—A single item general health measure will be used to measure patient health on a five-point Likert scale ranging from excellent to poor.
- **COPD duration**—The length of time since the patient was diagnosed with COPD will be recorded from less than 1 year, 1-5 years, 6-10 years, 11-19 years, or 20 or more years ago.
- **COPD treatment**—Patients will be asked to indicate their current COPD treatment.
- **Height**—Patients will be asked to provide their height in feet and inches. Total height in inches will be calculated.
- **Weight**—Weight in pounds will be collected.
- **BMI**—Body Mass Index will be calculated from patient report of height and weight. Patients will be assigned to one of four categories: Underweight ($<18.5 \text{ kg/m}^2$), Normal Weight (18.5-24.9 kg/m^2), Overweight (25-29.9 kg/m^2), or Obese ($\geq 30 \text{ kg/m}^2$).
- **Smoking behavior**
 - **Smoking status**—Status will be recorded as current smoker, former smoker, never smoked and lives with a smoker, or never smoked and no one in their household smokes.
 - **Cigarettes smoked per day, former smokers**—Former smokers will be asked to report how many cigarettes, on average, they smoked per day as an adult.
 - **Cigarettes smoked per day, current smokers**—Current smokers will be asked to report how many cigarettes, on average, they smoke per day.
 - **Pack year**—Pack year will be calculated by multiplying the total number of cigarettes smoked per day by the total number of years smoked, then dividing by 20 (1 pack has 20 cigarettes).
 - **Age started smoking**—Age in years.
 - **Age stopped smoking**—Age in years will be collected from former smokers.
 - **Total years smoked**—The number of years the patient has smoked will be calculated by subtracting patient-reported age when started smoking from age when quit smoking, or for current smokers, then subtracted from age at time of survey.

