11 APPENDIX 4. COVARIATES OF INTEREST FOR IPTW

The following is a list of covariates planned for inclusion in the IPTW analysis. Final covariates included in the multivariable models will be determined following review of the comparison of weighted and non-weighted descriptive results as described in Sections 4.3 - 4.4.

Clinical characteristics

- General health
- BMI
- Current smoking status
- Pack years
- Years since COPD diagnosis
- Baseline Quan-Charlson comorbidity score
- Count of COPD-related comorbid conditions
- Count of all-cause baseline medication fills
- Count of COPD-related baseline medication fills
- Count of all-cause baseline ambulatory visits (office and/or outpatient)
- Count of COPD-related baseline ambulatory visits (office and/or outpatient)
- Count of baseline COPD exacerbations

Demographic and sociodemographic characteristics

- Age
- Sex
- Race
- Ethnicity
- Geographic region
- Population density
- Marital status
- Household income
- Education

ⁱ Dillman DA. Mail and Internet surveys: the tailored design method, second edition. New York: John Wiley & Sons, Inc.

ⁱⁱ Edwards P, Roberts I, Clarke M, et al. Increasing response rates to postal questionnaires: systematic review. *BMJ*. 2002;324:1183.

ⁱⁱⁱ Following the Dillman tailored design method, Optum's standard data collection time period is 8 weeks.

^{iv} Doherty, DE, Belfer, MH, Brunton, SA, Fromer, L, Morris, CM, Snader, TC. Chronic Obstructive Pulmonary Disease: Consensus Recommendations for Early Diagnosis and Treatment. *J Fam Prac*, 2006.

^v Bestall C, Paul EA, Garrod R, et al. Usefulness of the Medical Research Council (MRC) dyspnea scale as a measure of disability in patients with COPD disease. *Thorax* 1999;54:581-586.

^{vi} Jones PW, et al. Development and first validation of the COPD Assessment Test (CAT). *Eur Respir J* 2009;34(3):648-654.

^{vii} Jones PE, et al. Properties of the COPD Assessment Test (CAT) in a cross-sectional European study. *Eur Respir J* 2012; doi: 10.1183/09021936.00177210.

^{viii} Quan H, Li B, Couris CM, Fushimi K, Graham P, Hider P, Januel JM, Sundararajan V. Updating and validating the Charlson comorbidity index and score for risk adjustment in hospital discharge abstracts using data from 6 countries. *Am J Epidemiol*. 2011;173(6):676-82.

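### Pack-years rest on an adult-average daily count for former smokers but, as described, on present consumption for current smokers, so the two groups are not on one scale

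*Combined protocol and SAP*

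**What the plan says.** Section 3.3.1.1 of the protocol describes the smoking items one line each.

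- Former smokers: "Former smokers will be asked to report how many cigarettes, on average, they smoked per day as an adult".
- Current smokers: "Current smokers will be asked to report how many cigarettes, on average, they smoke per day".
- Formula, the same for both groups: "Pack year will be calculated by multiplying the total number of cigarettes smoked per day by the total number of years smoked", with the product divided by 20.
- Years smoked: "subtracting patient-reported age when started smoking from age when quit smoking, or for current smokers, then subtracted from age at time of survey". The sentence is awkward, but its sense for current smokers is age at survey minus age at starting, that is, the whole smoking span.

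Appendix 4 (Section 11) introduces its entries thus: "The following is a list of covariates planned for inclusion in the IPTW analysis". Pack-years is on that list, and so, as a separate entry, is "Current smoking status". No section defines an adult-average item for current smokers, adjusts for a change in intensity, or remarks on the different time frames.

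**The concern.** Pack-years is meant to measure cumulative exposure. That requires the daily count to be an average over the same years by which it is multiplied. The former-smoker item comes close to this. The current-smoker item, in the present tense and with no adult or lifetime frame, does not: today's rate is carried back over every year since starting. A current smoker who has cut down is scored as a lighter lifetime smoker than is true, and one who has increased as a heavier one.

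Two uses are affected. First, the sample is non-random and unmatched (Section 3.2.2), so the plan relies on inverse probability weighting to control confounding, and pack-years is one of the two smoking terms in it. Section 4.5 bases the covariates of the outcome models on the weighting analysis, so the variable may carry forward. Second, smoking history is used to describe patients under the secondary objectives (Section 4.3), where a pooled pack-year distribution would mix two measures.

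The diagnostics in Section 4.4 (propensity overlap, goodness of fit, weighted against unweighted p values) would not reveal the problem, because a mis-scaled covariate can be balanced as well as a sound one. The survey is given once, so the missing information cannot be recovered afterwards.

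**Working it through.** The protocol states no pack-year figure, so there is none to reproduce. The check applies its rule to assumed smoking histories.

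**Inputs from the protocol.** The formula, the two intensity items and the definition of years smoked come from Section 3.3.1.1. The entry criterion "Age 65 and older" (Section 3.2.1.1) makes long smoking spans plausible.

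**Assumed inputs.** Age 70 at survey, started at 18, hence 70 − 18 = 52 years smoked without a break, and the daily counts in the table. None of these is in the documents.

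**Formulas.**

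- True exposure = sum over periods of (cigarettes per day × years) / 20.
- Protocol value, current smoker = present cigarettes per day × 52 / 20.
- Ratio of protocol to true = present rate / average rate over the smoking span, because the years and the 20 cancel.

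| Assumed history | True | Protocol | Ratio |
|---|---|---|---|
| 20/day throughout | 20×52/20 = 52.0 | 20×52/20 = 52.0 | 1.00 |
| 20/day, then 10/day for last 10 years | 42 + 5 = 47.0 | 10×52/20 = 26.0 | 0.55 |
| 20/day, then 10/day for last 5 years | 47 + 2.5 = 49.5 | 26.0 | 0.53 |
| 30/day, then 10/day for last 10 years | 63 + 5 = 68.0 | 26.0 | 0.38 |
| 20/day, then 5/day for last 10 years | 42 + 2.5 = 44.5 | 5×52/20 = 13.0 | 0.29 |
| 20/day, then 5/day for last 5 years | 47 + 1.25 = 48.25 | 13.0 | 0.27 |
| 10/day, then 20/day for last 10 years | 21 + 10 = 31.0 | 52.0 | 1.68 |

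**Same history, former smoker.** Take the second row. The average is (20×42 + 10×10)/52 = 940/52 = 18.1 a day. A former smoker who reports that average is scored 940/20 = 47.0, the true value. A current smoker with the identical history is scored 26.0.

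**A changed habit need not produce an error.** With 10/day for 20 years, 30/day for 20 and 20/day for the last 12, the average is (200 + 600 + 240)/52 = 20, equal to the present rate, and the protocol value is right. What matters is whether the present rate differs from the adult average, not whether the habit has ever changed.

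**What smoking status can and cannot do.** If all current smokers were off by the same amount, a status term would absorb it. Here the error is a person-specific factor, 0.27 to 1.68 in the table, so a status term takes up the average shift and leaves the rest.

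**The case against.** The strongest case against has four parts.

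1. **The questionnaire is not in the documents.** The reading depends on a one-line description, and a question to someone still smoking naturally takes the present tense. The item gives no reference period. This stands as a limit. If the booklet already asks for an adult average, the protocol text is what needs correcting. Section 4.2 leaves scoring instructions to the SAP, but scoring cannot supply an answer that was never asked for.
2. **The former-smoker value is itself approximate.** It rests on long recall, the adult average may not match a span that began before adulthood, and quit intervals are ignored. This is true, but recall and quit intervals affect both groups, and none of it justifies a second, avoidable difference between them.
3. **The large errors come from chosen histories.** This stands. They show what the rule can do and are not estimates for this sample, whose net direction is unknown.
4. **No effect on the drug comparison is shown.** Appendix 4 lists 21 covariates, among them smoking status, years since diagnosis, general health, comorbidity score and exacerbation count. A flawed covariate biases the weighted contrast only if true exposure is related to both drug choice and symptoms given the others. This also stands.

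A reader might infer that every current smoker whose habit has changed is mis-scored, or that the weighted CAT and mMRC comparison is biased. The first is refuted by the arithmetic. The second is not supported: nothing in the documents indicates that changes in smoking intensity differ between the UMEC/VI and FLUT/SAL cohorts.

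**Conclusion.** The concern holds in a limited form. As the items are described, pack-years is mis-scored for current smokers whose present rate differs from their adult average, and it is not comparable between current and former smokers. In the assumed histories the error runs from zero to roughly 70% in either direction. Its effect on the weighted comparison cannot be sized, because the documents give no share of current smokers by cohort and no smoking histories. The likely consequence is weaker control of confounding by cumulative exposure among current smokers, partly offset by the separate smoking-status term. No endpoint, hypothesis, sample size or eligibility rule is touched.

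The conclusion rests on the survey booklet matching the description in Section 3.3.1.1. The point merits action because the correction is small and the loss cannot be repaired once the survey has been fielded.

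**What to change.** Before the survey goes to the health plan's compliance review and the IRB (Sections 6.1.2 and 6.1.3), ask current smokers the same item as former smokers, for example: *On average, how many cigarettes per day have you smoked as an adult?* Use that answer in the pack-year formula for both groups, and keep present consumption only as a descriptor. State in Section 3.3.1.1 which item feeds the formula. The cost is one reworded or added item and no extra analysis. If the booklet is already under review, it must be resubmitted.

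If the item can no longer be changed, keep years smoked for all ever-smokers and let the pack-year term differ by smoking status in the propensity model (a status-by-pack-years interaction). Report pack-years separately for current and former smokers, with the difference in definition noted. This costs a few model terms. It does not remove the person-level error, but it stops the two scales from sharing one coefficient. Dropping pack-years for current smokers would be worse: it discards exposure information and leaves their value in the logistic model undefined.
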